The 95% confidence interval for the specificity and sensitivity will be calculated for both observers. For the confocal microscope to be concluded as having a specificity equal to that of the biopsy the lower limit of the 95% confidence interval must not be less than 94%. Similarly for sensitivity the lower limit of the 95% confidence must not be less than 92%. To assess the inter-observer agreement the Kappa statistic will be reported alongside the proportion of agreements and disagreements.

Sample size calculation

For a specificity of 97% with a maximum marginal error of 3% for constructing the 95% confidence interval a sample size of 125 is required. For a sensitivity of 95% with a maximum marginal error of 3% for constructing the 95% confidence interval a sample size of 203 is required. A total sample size of 328 will be required to test both a specificity of 97% and sensitivity of 95% with a marginal error of 3% for both.

Data management and analysis

The Clinical Record Forms (CRFs) must be completed, signed and dated by the Investigator or an authorised member of staff prospectively. The completed originals will be collected by the trials co-ordinator and held in the site file as source documents. It is the responsibility of the Investigator to ensure that CRFs have been completed correctly and that the data are accurate. Entries should be made in ballpoint pen and should be legible. Any errors should be crossed out with a single stroke, the correction inserted and the change initialled and dated. All missing and ambiguous data will be queried. The CRF may be amended as appropriate; this will not constitute a protocol amendment. The revised CRF should be used by all participating sites with immediate effect.

The data will be transferred anonymously to a password -secured electronic database. All patients will be pseudo-anonymised. Data will be stored in databases in the Dermatology Department, Skin Care Network, and any copies to be taken off site (for example for statistical analysis or for analysis by the equipment provider) will be anonymised and will be protected by encryption and password. Access will be restricted to medical and research personnel, and appropriate support personnel. Specific trial information will be restricted to Investigators and collaborators. The trial co-ordinator will be responsible for the daily administration of the database.

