An initial interim analysis of the data will be planned after 25 patients to ensure the RCM images are of sufficient quality to continue and complete the study. Data validation will be co-ordinated under the supervision of the trial statistician once the recruitment target has been reached. The final analysis and publication of results will be undertaken after all patients have been recruited. The accrual period is estimated to be 12 months but will be continued until sufficient numbers are obtained for the study to reach significance. Once the dataset is complete, assessment of the RCM images by the blinded investigators will take place to allow statistical analysis of the primary and secondary endpoints, namely specificity, sensitivity and kappa statistics. Analysis of the final dataset is expected to take place within 6 months of completion of accrual. Publication is expected within 12 months of completing the trial.

Ethical Issues

The study proposal is subject to approval by the appropriate Ethics Committee, and will adhere to Good Clinical Practice Guidelines. The study will be conducted according to the principles of the Declaration of Helsinki and in accordance with the Medical research Involving Human Subjects Act (WMO).

Amendments

Amendments are changes made to the research after a favourable opinion by the accredited Ethics Committees has been given. All amendments will be notified to the Ethics Committees that gave a favourable opinion.

A 'substantial amendment' is defined as an amendment to the terms of the Ethics Committee(s) application, or to the protocol or any other supporting documentation, that is likely to affect to a significant degree:

- the safety or physical or mental integrity of the subjects of the trial;
- the scientific value of the trial;
- the conduct or management of the trial; or
- the quality or safety of any intervention used in the trial.

All substantial amendments will be notified to the Ethics Committees and to the competent authority.

Non-substantial amendments will not be notified to the accredited Ethics Committees and the competent authority, but will be recorded and filed by the sponsor.

Annual Progress Report

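### The 328 total is a precision size: under the plan's own assumptions each pass limit is met about half the time or less, and a pass would not show that RCM equals biopsy

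*Combined protocol and SAP*

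**What the plan says.** The Sample size calculation section rests on interval width: "For a specificity of 97% with a maximum marginal error of 3% for constructing the 95% confidence interval a sample size of 125 is required", and "For a sensitivity of 95% with a maximum marginal error of 3% for constructing the 95% confidence interval a sample size of 203 is required". It then adds the two: "A total sample size of 328 will be required to test both a specificity of 97% and sensitivity of 95"%, and the sentence ends by repeating the 3% margin.

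The Summary of statistical methods sets a decision rule: "For the confocal microscope to be concluded as having a specificity equal to that of the biopsy the lower limit of the 95"% interval has to be at least 94%. For the other measure, "Similarly for sensitivity the lower limit of the 95% confidence must not be less than 92"%. It also says that "The 95% confidence interval for the specificity and sensitivity will be calculated for both observers".

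The Protocol Synopsis defines the primary endpoint as the sensitivity and specificity of RCM against standard histology. No power, null hypothesis or interval method is stated. The plan does not say whether both criteria must be met or which observer's result decides. Data management and analysis adds that accrual "will be continued until sufficient numbers are obtained for the study to reach significance".

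**The concern.** A sample size chosen to give a 3% half-width fixes how wide the interval is expected to be. It does not make it likely that the lower limit clears a mark placed exactly one half-width below the assumed value. To clear that mark, the observed proportion must come out at about the assumed value or better, which happens roughly half the time when the assumption is true.

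Three consequences follow.

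- **A miss is likely even if RCM performs as assumed.** A reader told that 328 is enough to test both quantities could take that miss as evidence against RCM.
- **The unnamed interval method can decide the result.** Near the pass mark, the same data pass under one common method and fail under another.
- **A pass would be overclaimed.** RCM is scored against histology from the biopsy, so biopsy has no sensitivity or specificity of its own in this study for RCM to equal. The wording matters because the Background suggests that accurate RCM could remove the need for a diagnostic biopsy in lower-risk patients.

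**Working it through.** **Inputs from the protocol.** Assumed specificity 97% and sensitivity 95%; half-width 3%; sizes 125 and 203, total 328; pass marks 94% and 92%; 95% intervals, taken as two-sided.

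**Assumptions added here.** One reader; one lesion per patient; all images evaluable; exactly 125 non-BCC and 203 BCC lesions; accrual stopped at 328.

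**1. Reproduce the stated sizes.** The Wald half-width formula is n = 1.96² × p(1−p) / d², with d = 0.03.

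- p = 0.97: 3.8416 × 0.0291 / 0.0009 = 124.2, so 125.
- p = 0.95: 3.8416 × 0.0475 / 0.0009 = 202.7, so 203.
- Total: 125 + 203 = 328.

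The figures match. The formula has no power term. The pass marks are 97 − 3 = 94 and 95 − 3 = 92.

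**2. Convert each pass mark to a maximum number of errors.** The table gives the lower 95% limit for results near the boundary.

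| Result | Wald | Wilson | Clopper-Pearson |
|---|---|---|---|
| 121/125 | 93.7% | 92.1% | 92.0% |
| 122/125 | 94.9% | 93.2% | 93.1% |
| 123/125 | 96.2% | 94.4% | 94.3% |
| 192/203 | 91.5% | 90.6% | 90.5% |
| 193/203 | 92.1% | 91.2% | 91.1% |
| 194/203 | 92.7% | 91.8% | 91.8% |
| 195/203 | 93.4% | 92.4% | 92.4% |

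Wald therefore allows at most 3 false positives and 10 missed BCCs. Wilson and Clopper-Pearson allow at most 2 and 8. Results of 122/125 and 193/203 pass under Wald and fail under the other two.

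**3. Chance of passing when the assumptions are true.** This is the exact binomial probability, with X the number of errors.

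- Wald: P(X ≤ 3 | 125, 0.03) = 48.1%; P(X ≤ 10 | 203, 0.05) = 56.4%.
- Wilson or Clopper-Pearson: P(X ≤ 2 | 125, 0.03) = 27.3%; P(X ≤ 8 | 203, 0.05) = 31.0%.
- If both criteria must be met (BCC and non-BCC lesions are separate groups, so the chances multiply): 0.481 × 0.564 = 27.1% with Wald; 0.273 × 0.310 = 8.5% with Wilson or Clopper-Pearson.

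**4. Chance of a false pass when the true value sits at the mark.** The nominal rate is 2.5%.

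- Wald: P(X ≤ 3 | 125, 0.06) = 5.4%; P(X ≤ 10 | 203, 0.08) = 6.2%.
- Wilson or Clopper-Pearson: P(X ≤ 2 | 125, 0.06) = 1.8%; P(X ≤ 8 | 203, 0.08) = 1.6%.

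**5. Other case mixes.** The protocol sets no quota for BCC and non-BCC lesions. The BCC shares of 328 below are assumed.

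| BCC share | BCC / non-BCC | Specificity, Wald | Specificity, exact | Sensitivity, Wald | Sensitivity, exact |
|---|---|---|---|---|---|
| 50% | 164 / 164 | 63% | 27% | 42% | 28% |
| 70% | 230 / 98 | 43% | 20% | 52% | 40% |
| 80% | 262 / 66 | 41% | 13% | 56% | 45% |

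Wilson gives the same chances as the exact limits in this table.

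**6. Scale of the shortfall.** Stepping through n, the chance stays at or above 80% per criterion from 333 non-BCC and 491 BCC lesions with Wald, and from 428 and 588 with Clopper-Pearson.

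**7. What a pass shows.** A lower limit exactly at the mark leaves up to 100 − 92 = 8% of BCCs missed, and 100 − 94 = 6% of non-BCC lesions called BCC, inside the interval.

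**The case against.** The best defence is that the plan is open about precision: all three sentences of the sample size section mention the 3% margin, and 125 and 203 are right for that purpose. Because they are Wald sizes, Wald is the natural reading of the intervals, and then the chance per criterion is about even; the lower figures appear only if another method is used. The joint figures describe a requirement that the plan never states. Accrual may also run past 328. Finally, the sensitivity shortfall depends on the assumed 95%: with true sensitivity of 97% and 203 BCCs, the chance of passing is 95.6% (Wald) or 84.1% (Wilson or exact), and the Background cites sensitivities up to 100%.

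These points limit the finding without removing it. The precision basis is stated, but the plan still attaches a conclusion to a threshold and never gives the chance of reaching it. The joint, case-mix and fixed-328 figures are conditional and should be read that way. Open-ended accrual does not define an adequate size. A higher true sensitivity does not help specificity, where the assumed 97% is already the top of the range that the Background cites. Wilson and Clopper-Pearson are somewhat conservative here, and other intervals fall in between: Jeffreys gives 27.3% for specificity and 43.6% for sensitivity. Wald, however, passes falsely at more than twice the nominal rate. That a miss would be read as failure is an inference, since the plan assigns no meaning to a miss.

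**Conclusion.** The concern holds. The 328 total is correct for a 3% half-width but is not a size that tests the stated limits. Under the plan's own assumptions, with one reader, a 125/203 split and accrual stopped at 328, each limit is met about half the time with Wald and less than one time in three with Wilson or Clopper-Pearson. No case mix examined between 50% and 80% BCC brings either chance to 80%. The equality wording is unsupported whatever the sample size, because histology is the reference. The missing joint rule and deciding reader are gaps in detail; the main conclusion does not depend on them. The estimates and their intervals remain usable, so this should be fixed but does not undermine the study's data.

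**What to change.** Four changes to the statistics section:

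1. Describe 328 as precision-based (3% half-width) and remove the statement that it is the size needed for a test. Give the single and joint chances of meeting the limits, with the conditions listed above.
2. Specify Wilson or Clopper-Pearson 95% limits.
3. Replace the claim of equality with biopsy by a statement that RCM meets pre-set performance goals of 94% specificity and 92% sensitivity against histology.
4. Before the images are read, state whether both criteria must be met and which reader's result decides. The choice of reader is for the study team.

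The cost is wording only, with no new patients or data. The downside is that the stated chance of success and the headline claim become less favourable, and Wilson or exact limits are harder to meet than Wald. The changes disclose the low chance of passing; they do not raise it.

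### The pass rule uses a 95% interval whose method is not named; the plan's figures come from the Wald formula, and the choice of method changes both the verdict and the false-pass rate

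*Combined protocol and SAP*

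**What the plan says.** Under Statistics, Summary of statistical methods, the plan states: "The 95% confidence interval for the specificity and sensitivity will be calculated for both observers". RCM may be concluded to have specificity equal to biopsy only if "the lower limit of the 95% confidence interval must not be less than 94" per cent. The rule for sensitivity is: "Similarly for sensitivity the lower limit of the 95% confidence must not be less than 92" per cent. The section does not say how either interval is to be calculated.

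Under Sample size calculation, the plan states: "For a specificity of 97% with a maximum marginal error of 3% for constructing the 95% confidence interval a sample size of 125 is required", and "For a sensitivity of 95% with a maximum marginal error of 3% for constructing the 95% confidence interval a sample size of 203 is required". The two sizes are added to give the recruitment target of 328. The formula behind them is not named. Each pass limit equals the assumed accuracy minus the 3-point margin (97 − 3 = 94 and 95 − 3 = 92).

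**The concern.** The conclusion depends on a single number, the lower confidence limit. For a proportion close to 100% with one to two hundred lesions, common interval methods place that limit in clearly different positions. The Wald interval is symmetric about the estimate and, in this range, sets its lower limit too high.

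The plan's figures come from Wald, but the plan does not say whether the analysis will use it. If it does, RCM can be declared equal to biopsy more often than a 95% interval suggests. If it does not, the stated 3-point precision is not achieved on the side that decides. If the matter stays open, the method could be settled after the counts are known. The Background section links the result to avoiding diagnostic biopsy before definitive treatment, so a wrong conclusion of equality would have consequences.

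**Working it through.** **Inputs, all from the Statistics section.** Two-sided 95% intervals, so a nominal 2.5% in the tail that decides. Specificity: design value 97%, margin 3 points, n = 125, limit 94%. Sensitivity: design value 95%, margin 3 points, n = 203, limit 92%. I take 125 as the number of non-BCC lesions and 203 as the number of BCC lesions on histology, one per patient.

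**1. Reproduce the sample sizes.** Wald precision formula: n = 1.96² × p(1 − p) / 0.03².

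- Specificity: 3.8416 × 0.97 × 0.03 / 0.0009 = 124.2, rounded up to 125.
- Sensitivity: 3.8416 × 0.95 × 0.05 / 0.0009 = 202.8, rounded up to 203.

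Both match. For a half-width of at most 3 points, other methods would need 145 and 215 (Wilson), 161 and 238 (Clopper-Pearson), 164 and 228 (Agresti-Coull) or 132 and 206 (Jeffreys). Of the methods tried, only Wald gives both stated figures.

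**2. Lower arm at the design values** (design value minus lower limit, with the observed proportion set equal to the design value).

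| | Wald | Wilson | Clopper-Pearson |
|---|---|---|---|
| Specificity 97%, n = 125 | 97 − 94.0 = 3.0 | 97 − 92.3 = 4.7 | 97 − 92.3 = 4.7 |
| Sensitivity 95%, n = 203 | 95 − 92.0 = 3.0 | 95 − 91.08 = 3.9 | 95 − 91.03 = 4.0 |

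**3. Lower limits near the pass boundary (%).**

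| Correct / n | Wald | Wilson | Clopper-Pearson |
|---|---|---|---|
| 121/125 | 93.7 fail | 92.1 fail | 92.0 fail |
| 122/125 | 94.9 pass | 93.2 fail | 93.1 fail |
| 123/125 | 96.2 pass | 94.4 pass | 94.3 pass |
| 193/203 | 92.1 pass | 91.2 fail | 91.1 fail |
| 194/203 | 92.7 pass | 91.8 fail | 91.8 fail |
| 195/203 | 93.4 pass | 92.4 pass | 92.4 pass |

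The smallest passing counts are therefore 122 and 193 by Wald, and 123 and 195 by Wilson or Clopper-Pearson.

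**4. Operating characteristics.** With X binomial(n, p) and c the smallest passing count, the false-pass chance is P(X ≥ c) at p equal to the limit. The pass chance is P(X ≥ c) at p equal to the design value.

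| | c | False pass | Pass at design value |
|---|---|---|---|
| Specificity, Wald | 122/125 | 5.4% | 48.1% |
| Specificity, Wilson or Clopper-Pearson | 123/125 | 1.8% | 27.3% |
| Sensitivity, Wald | 193/203 | 6.2% | 56.4% |
| Sensitivity, Wilson or Clopper-Pearson | 195/203 | 1.6% | 31.0% |

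**5. How often the verdicts differ.** At the design values, the chance of a result that passes by Wald and fails by the other two methods is 48.1 − 27.3 = 20.8 points for specificity (20.9 before rounding). For sensitivity it is 56.4 − 31.0 = 25.4 points.

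**6. Both limits together, per reader.** BCC and non-BCC lesions are different lesions, so the two chances multiply: 0.481 × 0.564 = 0.27 by Wald, and 0.273 × 0.310 = 0.085 by Wilson or Clopper-Pearson.

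**7. Sensitivity to n.** Specificity uses only non-BCC lesions, and recruiting 328 patients does not fix their number. With 130 of them the Wald false-pass chance is 4.4%, against 1.4% by Wilson or Clopper-Pearson. Over n = 100 to 150 in steps of 5, the Wald figure runs from 4.4% to 9.8%.

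**The case against.** The strongest reply is that planning with a normal approximation does not bind the analysis to it. The protocol names no analysis interval, and Data management and analysis refers to a trial statistician, who could compute an exact interval without departing from any sentence of the plan. This stands. A reader might infer that the plan's arithmetic fixes Wald as the analysis method and that the inflated error is therefore built in. The documents do not support that: they show Wald only through the planning figures. The inflation is conditional.

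A reader might also say that the error rate simply more than doubles. That needs a comparator and a sample size. At 125 lesions, 5.4% is 2.2 times the nominal 2.5%; at 130 lesions, 4.4% is less than twice nominal, though about three times the Wilson or Clopper-Pearson figure. Part of the gap is discreteness: at n = 125, allowing two errors gives 1.8% and allowing three gives 5.4%, so no cut-off gives exactly 2.5%.

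Nor is there a single valid alternative. The Jeffreys interval puts 194/203 at 92.07%, a pass, with a false-pass chance of 3.3%. The count of 195 follows from choosing Wilson or Clopper-Pearson.

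Finally, the case mix quoted in the Background for another study could be used to project far fewer non-BCC lesions and a much worse error rate. The plan does not say that this clinic shares that case mix, and a shortage of non-BCC lesions is a separate sample-size question. It is not relied on here.

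None of this makes the gap harmless. Under Wald the error rate is above nominal at the planned sizes; under Wilson or Clopper-Pearson the 3-point margin is not delivered.

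**Conclusion.** The point holds in conditional form. The method of the deciding interval is unspecified, while the sizes, margin and limits are Wald figures.

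- If Wald is carried into the analysis, the false-pass chance at the limit is 5.4% (specificity) and 6.2% (sensitivity), against a nominal 2.5% and against 1.8% and 1.6% with Wilson or Clopper-Pearson.
- If Wilson or Clopper-Pearson is used, the lower arm is about 4.7 points (specificity) and 3.9 to 4.0 points (sensitivity), not 3.
- The verdict differs between methods at 122/125 and at 193 or 194 of 203. At the planned accuracies such results have a chance of about 21% and 25%.

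These figures assume exactly 125 non-BCC and 203 BCC lesions, independent lesions, and one reader at a time. This is more than a missing detail because the choice of method can reverse the primary conclusion on the same data. It should be corrected before the images are read.

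**What to change.** In Summary of statistical methods, state that the sensitivity and specificity intervals are two-sided 95% Wilson (or Clopper-Pearson; choose one) intervals, and that the 94% and 92% limits apply to their lower limits. In Sample size calculation, restate the precision as lower arms of about 4.7 points for specificity and 3.9 points for sensitivity (4.0 with Clopper-Pearson). Give the counts needed to pass at the planned sizes: 123/125 and 195/203.

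The wording costs a few sentences and needs no new data. The downside must be disclosed. The chance of meeting each limit at the planned accuracy becomes about 27% and 31%, or about 8.5% for both together per reader. Under Wald it is 48% and 56%, or about 27% for both. The low figures arise because the study was sized for precision and not for the chance of passing.

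The sponsor should therefore also decide whether to recalculate the numbers for a stated chance of success. As a guide, an 80% chance of meeting each limit with a Clopper-Pearson interval needs about 428 non-BCC and 588 BCC lesions. If recruitment stays at 328, the plan should say plainly how unlikely a pass is even when its assumptions are true.

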Reflectance Confocal Microscopy (RCM) to diagnose basal cell carcinoma: HS-MAV-003

CHIEF INVESTIGATOR:

[name], MA (Oxon); MBBS; FRCP; PhD. Consultant Dermatologist,

Address and contact details:

Skin Care Network
[name]
[name]
[name]

Signature

Date 8-2-17

Sponsor:

Skin Care Network Barnet Ltd
[name]
[name]
[name]

Contents

Protocol Synopsis	3
Study Title:	4
Background.....	4
Aims.....	5
Study Design and Methods.....	5
Study Design	5
Study Hypothesis	5
Setting	5
Participants	5
Exclusion criteria	5
Informed Consent.....	5
Study Intervention	6
Statistics.....	7
Summary of statistical methods:.....	7
Sample size calculation.....	7
Data management and analysis	7
Ethical Issues	8
Amendments	8
Annual Progress Report	8
End of study report.....	8
Public disclosure and publication policy	8
Safety Considerations	9
Adverse and Serious Adverse Events (SAE).....	9
Follow-up of adverse events	9
Data Safety Monitoring Board.....	9
Sponsorship & Indemnity	9
Publication Policy	10
Data Safety Monitoring Board.....	10
References:	11
Appendix 1: Patient Information Sheet	Error! Bookmark not defined.
Appendix 2: Patient Consent Form	Error! Bookmark not defined.

Protocol Synopsis

Protocol ID	Version 0.5, 14 th February 2017
Protocol Title	HS-MAV-003
Development phase	II
Primary endpoint	Specificity & Sensitivity of RCM in diagnosing Basal Cell Carcinoma in non-pigmented lesions compared to standard histology
Secondary endpoint	Inter- & intra-observer agreement in assessing RCM images
Study design	This is a non-randomised, non-controlled, prospective observational study to look at the efficacy of in vivo RCM as a diagnostic tool in the diagnosis of BCC.
Key Inclusion Criteria	Patients 18 years or older with a suspected diagnosis of BCC
Key Exclusion Criteria	Recurrent or otherwise high-risk BCC Patient with basal cell naevus syndrome Patient treated with hedgehog inhibitor medication (vismodegib) Patient not suitable for diagnostic biopsy Location of lesion unsuitable, inaccessible or impractical for scanning with RCM as determined by investigator
Patient Accrual	328 patients over 18 months
Protocol follow-up procedure	None
Chief Investigator	[name]
Co-Investigators	[name], Dermatologie am Regierungsviertel Berlin.
Other key staff	[name] Consultant Dermatologist
Host Institution	Skin Care Network Barnet
Funding	None

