Should this diagnostic performance be shown to be replicable in an NHS setting, this would represent a significant opportunity to reduce waiting lists and save money, as patients with lower risk lesions could be diagnosed and treated during their first presentation to the skin cancer clinic. This would improve compliance

Recently, NICE guidance (Nov 2015) was issued regarding the use of RCM in the management of skin cancer [13]. They concluded the following:

“The VivaScope 1500 and 3000 imaging systems show promise but there is currently insufficient evidence to recommend their routine adoption in the NHS...”

“Further research...on using the VivaScope 1500 and 3000 imaging systems is recommended in the following areas:

...the impact on clinical workflows for melanoma and basal cell carcinoma assessment in secondary care settings.

...the number of confirmatory diagnostic biopsies needed for people with a clinical diagnosis of melanoma before definitive treatment is started."

If RCM is able to accurately diagnose basal cell carcinoma in the majority of lower risk patients then RCM would negate the requirement for diagnostic biopsy before listing patients for definitive treatment.

Aims

We propose to undertake a study to determine the diagnostic utility of using RCM for the diagnosis of Basal Cell Carcinoma (BCC) in a tertiary referral centre as outlined by the recent NICE report (Nov 2015). This will allow an assessment of the potential to avoid diagnostic biopsy within the treatment pathway.

Study Design and Methods

Study Design

This is an observational, non-randomised, non-controlled, prospective cohort study to look at the efficacy of *in vivo* RCM as a diagnostic tool in the diagnosis of BCC.

Study Hypothesis

The hypothesis of this study is that the use of RCM is would enable a reduction in the number of diagnostic biopsies taken before definitive treatment of BCC by at least 50%.

The secondary hypothesis is that the intra- & inter-observer agreement for interpreting the RCM images will have kappa scores 0.6 or greater (indicating good agreement).

Setting

Patients will be recruited from the outpatient clinic of Skin Care Network London.

Participants

The aim is to recruit 328 patients, who fit the following criteria:

1. Age 18 years or older.
2. Patient suspected of having a primary basal cell carcinoma that is a candidate for surgical treatment.
3. Patient willing and able to give informed consent.

Exclusion criteria

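### The inter-observer kappa hypothesis (0.6 or greater) has no confidence interval or decision rule, although sensitivity and specificity are judged on the lower 95% limit

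*Combined protocol and SAP*

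**What the plan says.** The Protocol Synopsis gives the secondary endpoint as "Inter- & intra-observer agreement in assessing RCM images". The Study Hypothesis section attaches a number to it: "intra- & inter-observer agreement for interpreting the RCM images will have kappa scores 0.6 or greater", which it describes as good agreement.

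The Summary of statistical methods treats the two kinds of endpoint differently.

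- **Accuracy:** "The 95% confidence interval for the specificity and sensitivity will be calculated for both observers". Success requires a lower limit of at least 94% for specificity and at least 92% for sensitivity.
- **Agreement:** "To assess the inter-observer agreement the Kappa statistic will be reported alongside the proportion of agreements and disagreements". No interval, test or rule for judging 0.6 follows.

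The Sample size calculation covers specificity (125) and sensitivity (203), total 328. It gives no precision or power for kappa.

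**The concern.** A numerical hypothesis needs a stated way of deciding whether it was met. For accuracy the plan asks that the data exclude values below the target. For kappa it offers only an estimate, so a reader of the results would naturally compare that estimate with 0.6. Agreement truly below 0.6 could then be presented as good through sampling error alone.

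Kappa also depends on case mix as well as on how well the readers perform. The plan does not fix the proportion of lesions with BCC. A single pooled kappa is therefore hard to interpret unless agreement is also shown separately for lesions with and without BCC.

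**Working it through.** **1. The plan's own figures.** With n = 1.96² p(1−p)/d² and d = 0.03:
- p = 0.97 gives 124.2, so 125
- p = 0.95 gives 202.7, so 203
- sum 328, as stated

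This is the Wald (simple normal) formula. The plan does not name an interval method.

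**2. Share of positive reads (assumed, since no prevalence is stated).**
- *About 60%:* at 203/125 and the planning accuracies, (0.95 × 203 + 0.03 × 125)/328 = 196.6/328 = 60%.
- *About 83%:* the Background quotes sensitivity 100% and 93%, specificity 78%, and positive predictive value 96% and 95% for the two probes. The BCC share is PPV(1−spec)/[PPV(1−spec) + (1−PPV)sens]. This gives 0.2112/0.2512 = 84% and 0.2090/0.2555 = 82%.

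**3. How often each rule would support the claim.** N = 328, both readers with the same positive rate, multinomial simulation, large-sample standard error of kappa (about 0.045 at 60% positive reads and 0.060 at 83%, for kappa 0.6).

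| True kappa | Positive reads | Estimate ≥ 0.6 | Lower 95% limit ≥ 0.6 |
|---|---|---|---|
| 0.55 | 60% | 14% | 0.2% |
| 0.55 | 83% | 20% | 0.4% |
| 0.75 | 60% | over 99% | 96% |
| 0.75 | 83% | over 99% | 81% |
| 0.80 | 60% | over 99% | over 99% |
| 0.80 | 83% | over 99% | 97% |

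The lower-limit rule needs an observed kappa of about 0.68 (62% positive reads) to 0.70 (83%).

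**4. What the accuracy limits imply for kappa at 203/125 (Wald).**
- Sensitivity: 10 misses in 203 give a lower limit of 92.1% (pass); 11 give 91.5% (fail).
- Specificity: 3 false positives in 125 give 94.9% (pass); 4 give 93.7% (fail).

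In the worst case the two readers never err on the same lesion. They then disagree on 2 × (10 + 3) = 26 of 328.
- Observed agreement: 302/328 = 0.9207
- Positive reads for each reader: (193 + 3)/328 = 0.5976
- Chance agreement: 0.5976² + 0.4024² = 0.5190
- Kappa: (0.9207 − 0.5190)/0.4810 = 0.835

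Wilson or exact limits allow 8 misses and 2 false positives, and the minimum is then 0.873.

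**5. Whether that bound is general.** It is not.
- *N = 328, Wald, 82-84% BCC:* minimum 0.71-0.73.
- *N = 328, Wald, 30 non-BCC lesions (298/328 = 91% BCC):* a reader passes with 16 misses (lower limit 92.1%) and no false positives. Agreement is 296/328 = 0.9024, positive reads are 282/328 = 0.8598, chance agreement is 0.7589, and kappa is 0.1436/0.2411 = 0.595.
- *N = 328, Wilson or exact:* the minimum stays at about 0.79. With fewer than about 60 non-BCC lesions the specificity limit cannot be met at all.
- *Accrual extended to 125 non-BCC lesions at 90% BCC:* minimum 0.54 (Wald) or 0.55 (Wilson or exact). The Data management and analysis section leaves accrual open-ended.

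**6. Case mix alone.** Take two readers at 95%/97% with independent errors. They agree on 0.95² + 0.05² = 0.905 of BCC lesions and 0.97² + 0.03² = 0.942 of the others.
- At 62% BCC: agreement 0.919, chance agreement 0.520, kappa 0.83.
- At 90% BCC: agreement 0.909, chance agreement 0.756, kappa 0.63.

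**The case against.** The plan says that kappa will be reported. It does not say that a point estimate of 0.6 will count as success, so that rule is inferred from silence. This stands: the accurate statement is that no rule is given and that the estimate is the only planned quantity to compare with 0.6.

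The point-estimate comparison also passes about 50% of the time at a true kappa of exactly 0.60. A reader might call that a false-claim rate. It is not, because the hypothesis is 0.6 *or greater* and is true there. The relevant figures are those below 0.6.

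Agreement is an unpowered secondary endpoint, and estimation with an interval but no pass mark would be a legitimate alternative. That is fair, but the plan does set a threshold, and it plans no interval for kappa.

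A reader might go further and infer that inter-observer kappa cannot fall below 0.6 once the primary criteria are met, and so adds nothing. The documents do not support this. The bound depends on BCC share, total number and interval method. The plan fixes neither the share nor the method, and accrual may continue past the target. The bound also needs both readers to meet both limits. The Background cites 78% specificity for both probes, so failure against a 94% limit is realistic, and kappa is then informative.

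Finally, where both readers pass at 203/125, the proposed rule would also be met: kappa is at least 0.835 with a standard error of about 0.03. The rule earns its place in the other cases.

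**Conclusion.** The gap is real and worth closing, though it touches only a secondary endpoint and no primary conclusion. The kappa hypothesis has a threshold but no interval or decision rule, in the same paragraph that sets lower-limit rules for accuracy. If the point estimate is what gets compared with 0.6, the claim would be supported in about 14-20% of trials at a true kappa of 0.55, against under 0.5% with a lower-limit rule. These rates assume 328 lesions read by both readers, equal positive rates, and 60-83% positive reads.

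At the planned 203/125 split with Wald limits, 0.6 is an undemanding threshold when both readers meet both accuracy limits. This is a statement about that split, not a property of the design. None of it bears on intra-observer kappa, the other half of the hypothesis, for which neither a repeat reading (Study Intervention) nor an analysis (Statistics) is described.

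**What to change.** In the Summary of statistical methods, replace the sentence on inter-observer agreement with:

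> Inter-observer kappa will be reported with its 95% confidence interval, and agreement of 0.6 or greater will be concluded only if the lower limit is at least 0.6. Observed agreement, with 95% intervals, will also be reported separately for lesions with and without BCC on histology.

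The change should be made before image reading begins. It needs no new data. The cost is a stricter claim: an observed kappa between 0.60 and about 0.68-0.70 would no longer support it. Power at a true kappa of 0.75 would be 96% with 60% positive reads but about 81% with 83%. At the planning accuracies and the 203/125 split, expected kappa is about 0.83 with a lower limit of about 0.77, so the rule would be met comfortably.

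This wording covers inter-observer agreement only. The intra-observer half needs its own repeat reading and analysis, or should be removed from the endpoint and hypothesis.
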